### **3.3.2 Effectiveness and Safety Analyses**

The endpoints will be analyzed with a paired t-test, which will compare baseline to 3-month post final treatment and 12-months post first treatment follow-up values. A p-value of <0.05 will be considered statistically significant. Adverse events will be categorized into medically relevant categories and presented as frequency counts and percentages. All results tables and plots shall clearly display the total number of patients in the analysis set (N) and the number of patients with evaluable data (n).

Output designs or minor changes in the tables may be adapted to programming and/or sponsor demands.

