3 Study Objectives

The objective of this post-marketing study is to advance the understanding of the mechanism of action of the CE marked RePneu Coil by observing changes in lung physiology and cardiac performance in patients with emphysema treated with the RePneu Coils, when used as intended.

Primary Endpoint:

Changes at 4 months post final treatment and 12 months post first treatment in:

- 6 Minute Walk Distance (6MWD)

Secondary Endpoints:

Changes prior and post procedure at Tx1, Tx2 and optional Tx3 in:

- Geometry (roundness) of major lung airways as defined by the ratio of major versus minor diameter measured from 3 bronchoscopic still images prior and post procedure taken in the lobar airway of the carina leading to segmental airways or while in any segmental airways of the same lobe of the carina leading to sub-segmental airways)
- Static and dynamic pulmonary compliance measurement prior to and post treatment including closing volumes, closing capacity and small airways function

Changes at 4 months post final bilateral treatment and 12 months post first treatment in:

- Physical activity and energy expenditure measured over a period of a week using multi-axial accelerometer.
- Forced expiratory volume in one second (FEV1)
- St. George's respiratory questionnaire (SGRQ)
- Residual volume (RV)
- Residual volume/total lung capacity (RV/TLC)
- Diffusion capacity (DLCO)
- mMRC dyspnea scale
- Cardiovascular parameters such as heart rate, heart ejection fraction, systemic blood pressure
- Body composition including BMI, fat per mass

Changes at 12 months post first treatment in:

- Ventilation and perfusion single photon emission tomography (V/P SPECT) or Quantitative lung perfusion scintigraphy (LPS)
- Diaphragm position during exhalation (Comparison of diaphragm apex to rib landmarks using frontal HRCT)
- Lung density distribution (post CT image data processing and reconstruction)

4 Study Design

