## 1 INTRODUCTION

### 1.1 Scope of this Document

This Statistical Analysis Plan (SAP) describes the planned statistical analysis of the RePneu study CLN0017. The SAP is based on the relevant sections of the protocol revision A (dated 19 August 2014) and the annotated eCRF (electronic Case Report Form) (dated 15 January 2018). This SAP was prepared based on the AMS Standard Operating Procedure ST-02.01.

The SAP contains a more technical and detailed elaboration of the principal features of the analysis described in the protocol. It includes detailed descriptions for executing the statistical analyses of all variables and describes how analyses are to be presented.

This SAP addresses both the safety listings during the ongoing study and the final analyses (see section 2 for the types of analyses planned). All versions of the SAP will be filed in the trial master file. Summary of changes and justification for each revision will be recorded in the version history. The SAP version used for the final analysis will be finalized prior to data base lock.

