7. Subject has an inability to tolerate bronchoscopy under moderate sedation or general anesthesia.
8. Subject has clinically significant bronchiectasis.
9. Subject has had previous LVR surgery, lung transplantation, lobectomy or other BLVR treatment in either lung.
10. Subject has participated in studies to treat COPD using high dose radiation.
11. Subject has been involved in pulmonary drug or device studies within 30 days prior to this study.
12. Subject is chronically taking >20 mg prednisone (or equivalent dose of a similar steroid) daily.
13. Subject requires high level chronic immunomodulatory therapy to treat a moderate to severe chronic inflammatory autoimmune disorder.
14. Subject is on any type of antiplatelet or anticoagulant therapy which cannot be stopped for seven (7) days prior to procedure.
15. Subject has a sensitivity or allergy to Nickel.
16. Subject has a known sensitivity to drugs required to perform bronchoscopy.
17. Subject has been diagnosed with alpha-1 antitrypsin deficiency (AATD).
18. Subject has any other disease, condition(s) or habit(s) that would interfere with completion of study and follow-up assessments, would increase risks of bronchoscopy or assessments, or in the judgment of the investigator would potentially interfere with compliance to this study or would adversely affect study outcomes.

It was planned to enroll 60 patients into two sites which should be bilaterally treated. Due to an early termination of the study the total number of enrolled patients will not be as high as planned.

The follow up visits shall be performed 1 month post each procedure and then 3 months post final treatment. The final study follow up visit shall be performed 1 year post first treatment.

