**Primary Endpoint:**

Changes at 3 months post final treatment and 12 months post first treatment in:

- 6 Minute Walk Distance (6MWD)

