### **5.6.1 Primary effectiveness endpoint**

Changes at 3 months post final treatment and 12 months post first treatment in:

- Minute Walk Distance (6MWD)

The change from baseline as continuous variable and the responder analysis as categorical variable will be presented.

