### **5.6.2 Secondary effectiveness endpoints**

Due to the small sample size, the secondary effectiveness endpoints will only be listed. The assessments and change from baseline will be presented per patient in the efficacy listing.

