## APPENDIX I: OVERVIEW OF TABLES, FIGURES AND LISTINGS TO BE PRODUCED

### Overview of planned tables

Programmer Note: Please adapt the numbering of subgroup tables as may be necessary.

Table Number	Title	Analysis Set for Final Analyses	Subgroup Analyses 
14.1.1	Patient accountability	ITT	No
14.1.2	Study terminations	ITT	No
14.2.1	Enrollment by site	ITT	No
14.2.2	Demographics	ITT	No
14.2.3	Baseline characteristics	ITT	No
14.2.4	Medical history	ITT	No
14.2.5	History and characterization of emphysema	ITT	No
14.2.6	Treatment of emphysema	ITT	No
14.3.1	Number of devices implanted	ITT	No
14.3.2	Procedure time	ITT	No
14.3.3	Post-procedure hospital stay	ITT	No
14.6.1	Adverse events	ITT	No
14.6.2	Serious adverse events	ITT	No
14.6.3	Device and procedure related adverse events	ITT	No
14.7.1	Change from baseline in 6MWT in m	ITT	No
14.7.2	Number and percentage of patients achieving change in 6MWT in m $\geq 25$	ITT	No

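### Do the two unadjusted tests of the primary 6MWD change, at 3 and 12 months, need a multiplicity rule?

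*SAP*

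**What the plan says.** SAP 1.3 gives one primary endpoint, 6MWD, at two times: "Changes at 3 months post final treatment and 12 months post first treatment in". Protocol section 3 has the same structure with a different first visit: "Changes at 4 months post final treatment and 12 months post first treatment in". SAP section 4 records the move from 4 to 3 months as a deliberate change.

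The test is in SAP 3.3.2 (and, with 4 months, in protocol 4.6): a paired t-test that will "compare baseline to 3-month post final treatment and 12-months post first treatment follow-up values. A p-value of <0.05 will be considered statistically significant".

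For the primary endpoint, SAP 5.6.1 adds only this: "The change from baseline as continuous variable and the responder analysis as categorical variable will be presented". For the rest, SAP 5.6.2 says: "Due to the small sample size, the secondary effectiveness endpoints will only be listed". In Appendix I, Table 14.7.1, "Change from baseline in 6MWT in m", is the only planned table of change from baseline. Table 14.7.2 counts 6MWT responders, and no test is stated for it.

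The setting is in SAP 1.2: "Due to an early termination of the study the total number of enrolled patients will not be as high as planned".

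**The concern.** With the secondary endpoints reduced to listings, the 0.05 threshold in practice governs two tests: 6MWD at the first follow-up and 6MWD at 12 months. Both carry the label of primary endpoint, and the plan does not say how they combine. If the report could call the primary result positive because one of the two visits reached p<0.05, whichever it was, there would be two chances to succeed under the null. The error rate for that claim would exceed that of a single test. Choosing the visit after seeing the data is what a prespecified rule normally prevents.

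**Working it through.** The documents give no power calculation, overall error rate or derived figure, so there is nothing of the plan's own to reproduce beyond the 0.05 per test.

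**Inputs**
- Number of tests: 2, for 6MWD at the two visits (SAP 1.3, 3.3.2, 5.6.1).
- Threshold: 0.05 per test (SAP 3.3.2). Sidedness is not stated. Two-sided is assumed, so each test carries 0.05/2 = 0.025 in the direction of improvement, with critical value 1.960.
- Correlation ρ between the two change scores: not given. Assumed range 0 to 0.95.
- Sample size: 60 planned (protocol 4.2); the final number is lower and not given. Values of n below are illustrative.

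**Plausible ρ.** Both changes use the same patients and subtract the same baseline. If the three measurements have equal variance σ² and equal pairwise correlation c, then each change has variance 2σ²(1−c) and their covariance is σ²(c − c − c + 1) = σ²(1−c). Hence ρ = 1/2 whatever c is. Values of 0.5 and above are therefore more plausible than 0.

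**Either-visit rule, no true change**

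P(at least one significant improvement) = 0.025 + 0.025 − P(both), with P(both) from the bivariate normal distribution.

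| ρ | P(both) | P(at least one) |
|---|---|---|
| 0 | 0.0006 | 0.0494 |
| 0.5 | 0.0046 | 0.0454 |
| 0.7 | 0.0083 | 0.0417 |
| 0.9 | 0.0148 | 0.0352 |
| 0.95 | 0.0177 | 0.0323 |

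At ρ = 0 this is also 1 − 0.975² = 0.0494. Simulated paired t-tests agree: at n=10, 4.64% for ρ=0.5 and 3.58% for ρ=0.9; at n=60, 4.56% and 3.57%. If the tests were one-sided at 0.05, the reference would be 5% and the zero-correlation figure 1 − 0.95² = 9.75%.

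**Other readings**
- Both visits required: the error is the P(both) column, from 0.06% to 1.77% over this range, and never above 2.5%.
- Each p-value read for its own visit: 2.5% in the direction of improvement at each visit, as stated.
- A named lead visit or a fixed testing order: 2.5%.

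Only the either-visit rule inflates the error.

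**Cost of adjusting.** Holm's procedure compares the smaller p-value with 0.025 first. That brings the improvement error to 2.32% at ρ=0.5 and 1.65% at ρ=0.95. The first-step critical value rises by 2.241/1.960 = 1.14, or by 2.685/2.262 = 1.19 for a t-test at n=10. At n=10, with an assumed standardised change of 0.8 at both visits and ρ=0.5, the chance of at least one significant visit falls from 78.5% to 65.5%, a loss of 13 percentage points.

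**The case for a change.** The best argument for a change is that the SAP did not make 6MWD descriptive. It cut the secondary endpoints to listings because of small numbers, yet kept a designated primary endpoint and an explicit significance threshold. A plan that keeps a threshold should say what crossing it supports. The word joining the two visits lists when change is measured; it is not a success rule. Presenting both results does not settle which one carries a claim. One sentence would close the gap, and SAP 1.1 leaves a route: "The SAP version used for the final analysis will be finalized prior to data base lock".

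Part of this stands. The omission is real, the arithmetic is right, and a report that declared a positive primary result on one visit alone would overstate its evidence.

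The rest does not carry as far as a change. The threshold is attached to a p-value, not to trial success, and no passage says one visit suffices. The sentence is also less neutral than it looks. Holm presupposes that a single visit can support a claim; a both-visits rule, a lead visit, a fixed order and a purely descriptive reading would each close the same gap with different consequences. In a small, early-terminated study the descriptive reading fits at least as well as Holm and costs no power. Finally, the error at issue concerns change from baseline in an uncontrolled, open-label cohort. Regression to the mean and the medication changes that protocol 4.7.3 allows would remain after any adjustment, so tighter control of this error would not turn the result into evidence of device benefit.

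**Conclusion.** The plan leaves an interpretation rule unwritten, but following it as written produces two visible results, each valid at its own threshold. The excess error arises only under an either-visit claim that neither document makes. It would then be about 0.7 to 2.0 percentage points above 2.5% (3.23 − 2.50 to 4.54 − 2.50) for correlations of 0.95 down to 0.5, and at most 2.4 points (4.94 − 2.50) at zero correlation. These sizes rest on two-sided tests and an assumed correlation, since the documents give neither.

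The stated objective is to observe changes and learn about mechanism, with no hypothesis of success, power target or overall error rate to protect. An analyst will sensibly report both visits with their own p-values and make no combined claim. Imposing a particular adjustment is a choice on which reasonable statisticians would differ, with a visible loss of power at small n. No change to the plan is needed.

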### **3.3.3 Listings**

Listings will be sorted by patient and visit, if applicable. All listings will include unique subject identifier (subject ID). Individual listings may be subdivided into several smaller listings, if deemed sensible for manageability during programming.

## **3.4 Missing/Inconsistent Data**

### **3.4.1 Imputation**

Analyses will be based upon observed data without imputation.

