4.6 Statistical analysis

The endpoints will be analyzed with a paired t-test, which will compare baseline to 4-month post final treatment and 12-months post first treatment follow-up values. A p-value of <0.05 will be considered statistically significant. Parametric descriptive statistics will be used to summarize data for secondary effectiveness variables. Adverse events will be categorized into medically relevant categories and presented as frequency counts and percentages.

Intention to Treat (ITT) and Per-protocol analyses will be performed as well as a site-specific subgroup analysis.

Other subgroup analyses will include:

- upper vs. lower lobe treatments
- multi-variate analysis of baseline characteristics, adverse events, and various CT and other imaging characteristics

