#### 3.3.1 Descriptive statistics

Continuous variables will be displayed including arithmetic mean, standard deviation (SD), minimum (min), median and maximum (max). Additionally, the number of patients in the analysis set (ITT), those contributing to the analysis (N) and the number of patients not included in the analysis due to missing data (missing) will be displayed.

The Change from Baseline will be calculated for each patient individually and averaged for values at baseline (mean, SD, min, median, max at baseline), values at each visit (mean, SD, min, median, max at visit) and the change from baseline to each visit.

Categorical variables will be displayed as frequencies and percentages (i.e. absolute and relative frequencies). If not specified otherwise, the percentages will be based on all patients respectively procedures available for analysis (non-missing and missing). The number of patients with missing data will also be summarized.

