### 5.2 Study Patients

A listing with general information on the study patients will be provided, including:

- Study site
- Informed consent date
- Termination date and reason for discontinuation (if applicable)
- Death (yes/no) and, if yes, death date and whether death is emphysema related or unrelated to emphysema

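### The 6MWD mean change and p-value use only patients with a follow-up walk, so losses through death or illness can bias the primary result towards benefit, and no sensitivity analysis would show it

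*SAP*

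**What the plan says.** The primary endpoint is 6MWD: "Changes at 3 months post final treatment and 12 months post first treatment in" (SAP 1.3). On the method, SAP 3.3.2 says "The endpoints will be analyzed with a paired t-test" and adds "A p-value of <0.05 will be considered statistically significant". On missing data, SAP 3.4.1 says only "Analyses will be based upon observed data without imputation".

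The analysis set in SAP 3.1 is every subject who met the entry criteria, and SAP section 4 brings in those treated on one side only. Table 14.7.1 (mean change) and Table 14.7.2 (share gaining at least 25 m) are both labelled ITT.

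The SAP does make losses visible:
- 3.3.1 and 3.3.2 require the analysis-set count, the evaluable count and the number missing.
- 5.2 and 5.2.1 list deaths, and discontinuations with their reasons.
- 5.2.2 lists loss to follow-up and missed 3-month and 12-month visits.
- 3.3.1 bases percentages on all patients, missing ones included, unless stated otherwise.

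Neither document gives a value or rule for a patient who died or could not walk, a field for why a walk is missing, or a sensitivity analysis.

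**The concern.** A paired t-test needs both a baseline and a follow-up value, so under an observed-data rule the primary mean and p-value describe only those who returned and walked. In this population some losses could plausibly be linked to the outcome. Entry requires FEV1 at or below 45% predicted and mMRC of at least 2. The protocol's own history (section 2.3, Table 2) reports serious COPD exacerbation or pneumonia in 41/238 procedures (17.2%) and serious pneumothorax in 14/238 (5.9%) up to 6 months, and each patient is planned to have two or three procedures. A patient who stops after one procedure stays in the ITT set but leaves the test unless a follow-up walk is done.

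The study is single-arm, so no comparator suffers the same loss and the mean change is read by itself. The two primary tables also treat the same missing patient differently: counted in the responder denominator, absent from the mean.

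**Working it through.** **The plan's own figures.** There is no power calculation, SD, dropout rate or baseline 6MWD to reproduce. The planned size is 30 per site x 2 sites = 60, and SAP 1.2 says fewer were enrolled without giving the number. The historical death rate reproduces: 2/238 = 0.84%, stated as 0.8%.

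**Inputs from the documents.** 12-month 6MWD changes of +34.1 m and +51.4 m (Protocol 2.3, Table 1), and the 25 m responder threshold (SAP 5.6).

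**Assumed inputs.** Those two changes are observed-case means; share lost to death or illness m = 5% or 10%; baseline 300 m (range 250 to 350 m), so that a follow-up scored 0 m is a change of -300 m; as a milder case, a change of -50 m. Change is taken per patient, as SAP 3.3.1 describes.

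**Effect on the mean.** All-patient mean = (1 - m) x observed mean + m x mean change in the missing.

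| Share missing, their change | Observed +34.1 m | Observed +51.4 m |
|---|---|---|
| 5%, -300 m | 0.95 x 34.1 - 15 = +17.4 | 0.95 x 51.4 - 15 = +33.8 |
| 10%, -300 m | 0.90 x 34.1 - 30 = +0.7 | 0.90 x 51.4 - 30 = +16.3 |
| 10%, -50 m | 0.90 x 34.1 - 5 = +25.7 | 0.90 x 51.4 - 5 = +41.3 |

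**Tipping share.** m = (observed - target)/(observed - mean change in the missing). With a 300 m baseline and 0 m scoring:
- Below 25 m: 9.1/334.1 = 2.7% and 26.4/351.4 = 7.5%. Over baselines of 250 to 350 m: 2.4-3.2% and 6.6-8.8%.
- To zero: 34.1/334.1 = 10.2% and 51.4/351.4 = 14.6%. Over the same baselines: 8.9-12.0% and 12.8-17.1%.

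**Can one loss reverse the sign?** It needs (N - 1) x observed mean < 300. At +34.1 m, N - 1 < 8.8, so N of 9 or fewer. At +51.4 m, N - 1 < 5.8, so N of 6 or fewer.

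**Effect on the test.** Simulation with no true change, two-sided 0.05, 20,000 runs per setting, assumed SDs of change of 50 and 80 m. The rate of false findings of benefit should be 2.5%.

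| Which 10% are missing | N = 15 | N = 60 |
|---|---|---|
| Only below-average changers can be missing | 5.1-5.5% | 9.5-9.8% |
| Always the worst changers | 9.4-9.5% | 36.9-37.1% |

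When missingness is unrelated to the change, the rate stays at 2.3-2.7% in all settings. N = 15 is an assumption, and N = 60 was not reached.

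**Responder table.** If half of the evaluable patients respond and 20% are missing, the all-patient denominator gives 0.8 x 50% = 40%. That table is already conservative; the mean is not.

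**The case against.** A reader might infer that patients drop out silently, that the result is biased, and that one or two losses would reverse it. The documents do not support any of these as stated.

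- **Not silent.** Counts, missed visits, deaths and discontinuations are all shown, and Listing 16.6 gives values per patient. In a small study a reader can largely see who is absent. This stands, but disclosure does not alter the mean or the p-value.
- **Direction depends on the reasons.** The documents do not say why walks will be missing. The study stopped early for slow recruitment, so some missing visits could be administrative. This stands: the claim can only be conditional.
- **Rates are assumed.** The only mortality figure is 2/238 procedures to 6 months, or about 1.7% per patient if each had two procedures (an assumption). Deaths alone may be too few to matter, so illness and withdrawal may weigh more. This stands, and it is why the figures above are illustrations.
- **Sign reversal.** Under the illustration's inputs, one loss reverses the sign only in a study of 9 patients or fewer, and the final N is not given.
- **Weight.** The objective is to observe changes and understand mechanism, and an uncontrolled change is not a clean treatment effect even with complete data. True, but 6MWD is still the named primary endpoint, with a significance threshold attached.

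**Conclusion.** The concern holds in conditional form. As written, the SAP gives a primary mean and p-value that are too favourable whenever walks are missing because of death or being too ill to walk, and no planned analysis would show by how much. If no walks are missing, or the reasons are unrelated to health, there is no bias.

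The size cannot be fixed from the documents, because final N, dropout, SD and baseline 6MWD are not given. Under the assumptions above, 5% to 10% informative loss scored 0 m lowers the mean by about 17 to 35 m, and a milder -50 m change in 10% lowers it by about 8 to 10 m. The SAP's own responder threshold is 25 m, so shifts of this size could change how the result is read. The gap is worth closing before database lock, while the rule can still be set without knowing whom it affects.

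**What to change.** Keep the observed-case Table 14.7.1 unchanged and add one sensitivity row at each time point (3 months after final treatment, 12 months after first).

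- **Who.** Patients with no 6MWD because of death or documented inability to walk from illness. All other missing walks stay missing.
- **Test.** A one-sample signed-rank test ranks absolute changes, so "worst rank" must be defined. Give these patients a change more negative than the largest observed absolute change, so that they take the largest negative signed ranks. Report the Wilcoxon signed-rank p-value and the median.
- **Mean.** In the same row, add the mean with their follow-up walk scored 0 m, because one or two losses barely move a median.
- **Table 14.7.2.** Confirm that the all-patient denominator of SAP 3.3.1 applies. This largely restates the plan, but SAP 5.3 uses the non-missing denominator for baseline data, so a line is worth having.
- **Listing 16.6.** Show the reason for each missing walk, taken from the death, discontinuation and AE data already collected, marked unknown where none was recorded. No new eCRF field is needed.

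The cost is a little programming and a possibly less favourable figure beside the main one. If no patient meets the definition, the row uses the same patients as the main analysis.
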